STUDY PROTOCOL

Urinary Infection and Colonization in Bone Procedures

Version March 2025

POPULATION:

For seniors aged 65 and over undergoing surgery (bone procedures, traumatology, orthopedics) in acute or elective mode, the relationship between preoperative urinary tract infection/colonization (within 30 days before the procedure) and the occurrence of predefined postoperative complications will be monitored (during the hospitalization period of patients). Among the monitored signs before surgery will be urine collection (chemical + sediment - a common part of pre-anesthetic examination), in case of findings, collection for bacteriological examination will be indicated. Furthermore, subjective complaints (present, absent), presence of fever, whether the infection/findings in the urine were treated or not, performance of control urine examination (performed, not performed).

The Clinical Frailty Scale and any administered antibiotic treatment will be recorded. After the surgical procedure, the occurrence of urinary infection (yes, no, sample not taken) will be assessed.

Postoperative complications such as fever, circulatory instability, delirium development, infection occurrence, sepsis development, and death will be monitored. The patient's trajectory during hospitalization (which departments they will be treated in, including the length of hospitalization) will be recorded.

The primary objective will be to determine the relationship between the preoperative occurrence of urinary infection or colonization in patients within the last 30 days before the procedure and the occurrence of predefined postoperative complications. The secondary objectives will be to determine the most common postoperative complication in patients with preoperative urinary colonization and in patients with proven urinary infection. Additionally, the relationship between the preoperative Clinical Frailty Scale score in the defined patient population and the occurrence of predefined postoperative complications will be assessed. The final secondary objective will be to determine preoperative antibiotic therapy in the preoperative period.

The cohort of trauma patients undergoing surgery was chosen to ensure the homogeneity of the studied population (seniors aged 65 and over undergoing bone surgery).

TYPE OF STUDY:

- monocentric, prospective, comparative, observational

CHARACTERISTICS OF THE EVALUATION SUBJECT GROUP (AGE STRUCTURE, GENDER, METHOD OF RECRUITMENT, REWARD FOR PARTICIPATIONS, etc):

- Elective trauma procedures for seniors aged 65 and over, including acute trauma procedures for seniors aged 65 and over.
- Women and men.

- Recruitment at the time of indication for the procedure or setting the date of surgery, as part of the pre-anesthetic examination.
- No reward for participation
-

PRIMARY OBJECTIVE:

- The primary objective will be to determine the relationship between the preoperative occurrence of urinary infection or colonization in patients within the last 30 days before the procedure and the occurrence of predefined postoperative complication

SECONDARY OBJECTIVE:

- To determine the most common postoperative complication in patients with preoperative urinary colonization.
- To determine the most common postoperative complication in patients with proven urinary infection.
- To determine the relationship between the preoperative Clinical Frailty Scale score in the defined patient population and the occurrence of predefined postoperative complications.
- To determine preoperative antibiotic therapy in the preoperative period.

ENTRY CRITERIA

- Age over 65 years, including.
- Elective or acute trauma/orthopedic bone surgery.
- Urine examination as part of pre-anesthetic examination, urine + sediment, in case of suspicion - bacteriological examination (common part of pre-anesthetic examination).
- Signed informed consent for research as part of pre-anesthetic examination (I or II), respecting informed consent as an expression of the patient's "free will".

EXCLUSION CRITERIA

- Negative urine findings: chemical + sediment examination preoperatively
- Respondent under the influence of premedication, alcohol, or drugs
- Sensory impairment (blindness)
- Delirious preoperative state
- Severe mental disorder
- Sopor
- Coma
- Septic state
- Acute respiratory failure
- Disagreement with participation in the study

MONITORED SIGNS BEFORE SURGERY

- be urine collection (chemical + sediment - a common part of pre-anesthetic examination)

- in case of positive findings (bacteriuria, pyuria, leukocyturia), collection for bacteriological examination will be indicated.
- subjective complaints (present, absent) presence of fever,
- whether the infection/findings in the urine were treated or not
- performance of control urine examination (performed, not performed)
- antibiotic therapy (yes, no, what kind of antibiotic treatment)
-

MONITORED SIGNS AFTER SURGERY

- Temperature, fever
- Circulatory instability (
- Infection development, origin
- Sepsis development, origin
- Delirium development (standard procedure), scale (CAM-ICU)
- Patient trajectory during hospitalization
- Administered antibiotic treatment and its duration
- Respondent morbidity
- Respondent mortalit

STATISTICAL ANALYSIS PLAN

- Data will be evaluated in collaboration with a statistician

All patient data will be pseudo-anonymized, and patients will be assigned a number. This project does not differ from the standard procedure in practice in Tomas Bata Hospital Zlín, Czech Republic.

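### A urinary infection or fever already present before surgery can be counted as a postoperative complication, because the recorded items do not separate new from persisting

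*Protocol*

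**What the plan says.** The exposure, under PRIMARY OBJECTIVE, is "the preoperative occurrence of urinary infection or colonization in patients within the last 30 days before the procedure". One secondary objective asks which complication is most frequent among patients whose urinary infection was proven.

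On outcomes, the POPULATION section says: "Postoperative complications such as fever, circulatory instability, delirium development, infection occurrence, sepsis development, and death will be monitored". The preceding paragraph adds a separate item: "After the surgical procedure, the occurrence of urinary infection (yes, no, sample not taken) will be assessed". The list under MONITORED SIGNS AFTER SURGERY has "Temperature, fever" and "Infection development, origin".

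On the state before surgery, EXCLUSION CRITERIA removes patients with "Delirious preoperative state" and those who are septic. It names neither urinary infection nor fever. It does remove patients with a negative urine result, so every enrolled patient has a positive urine finding. MONITORED SIGNS BEFORE SURGERY lists "subjective complaints (present, absent) presence of fever", whether the urinary finding was treated, antibiotic therapy, and "performance of control urine examination (performed, not performed". No item is listed for the result of that control examination.

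**The concern.** For delirium and sepsis the protocol secures a clean start: the condition is excluded beforehand, so any later case is new. For urinary infection and fever it does not. The first is itself part of the exposure and the second may be one of its signs. If either continues through surgery and is recorded afterwards, the exposure, or its fever, is counted as its own consequence.

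Two results are at stake. The primary association could partly reflect carry-over and not an effect on postoperative events. The description of complications among patients with proven urinary infection could partly report the condition that put them in that group.

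**Working it through.** The protocol states no sample size, event rate or effect size, so there is no figure to reproduce. The check sets the items side by side, then uses one identity to see what can be said about direction.

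**Step 1: state before surgery against the outcome item.**
- *Delirium and sepsis:* excluded beforehand and worded as developing afterwards. New onset is secured.
- *Fever:* not excluded. It is recorded before surgery and again after it, but the later item does not refer to the earlier one. A new-fever variable could be derived from the two records; the rule for doing so is not stated.
- *Urinary infection:* an exposure and not excluded. None of the three postoperative levels separates new from persisting infection.
- *Infection in general:* the POPULATION section speaks of occurrence, the later list of development with origin. The second suggests onset, but neither gives a criterion for an infection already present.

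**Step 2: can the listed urinary items tell two histories apart?** Take two patients, both with proven urinary infection inside the 30-day window, both treated, and both with a control urine examination.
- Patient A: the control is clear, and a new urinary infection arises after surgery.
- Patient B: the control is still positive, and the same infection is found after surgery.

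On these items both read: exposed, treated, control performed, postoperative urinary infection present. The one fact that differs before surgery is the control result, and it is not a listed item. It may exist in the hospital record, but the protocol does not provide for collecting it.

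**Step 3: direction.** In any group, let p be the rate of new events and q the share in whom the preoperative condition persists and is counted. Then

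counted rate = q + (1 − q)p

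excess over the rate of new events = q + (1 − q)p − p = q(1 − p)

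Within one group the excess cannot be negative, so the counted frequency of urinary infection or fever is too high whenever q is above zero. Between two groups with the same p and persisting shares q₁ and q₀, the difference in rates is shifted by

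q₁(1 − p) − q₀(1 − p) = (q₁ − q₀)(1 − p)

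The sign depends on which group has more persisting cases. The protocol does not state the contrast for the primary objective, and with negative urine excluded it describes no comparison group free of urinary findings. It gives no value for p, q₁ or q₀. Neither sign nor size follows from the document.

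**The case against.** The strongest reply is that this is outcome derivation, which an analysis plan not shown here may settle. For fever that largely stands: both records are listed, and a rule could be written later. For urinary infection it does not. The levels of the postoperative item are fixed in this protocol, and no analysis rule can recover a control result that was not collected.

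A second reply is that the list of postoperative signs already speaks of infection developing, with its origin. That also stands in part. It makes the gap narrower for infection in general and leaves it clearest for fever and for infection of urinary origin. The two wordings may well be meant alike; aligning them costs one edit.

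Third, the urinary infection item sits apart from the named complications, so it may not be meant as one of them. That is fair: the protocol does not say. Even so, a urinary infection could still enter through the general infection item.

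Fourth, excluding septic patients removes some infected or febrile patients. It does not remove all of them.

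A reader might infer that the primary association is biased upwards, or that a false positive finding is likely. The document does not support this. Such a conclusion needs a comparison group with less carry-over, plus event rates and group sizes, and none of these is given. A reader might also infer that infection would wrongly rank as the most frequent complication. That does not follow either: fever could be inflated by the same route, so the order of the two cannot be predicted. Nor is fever the only complication without onset wording or a matching exclusion. Circulatory instability lacks both, and no claim is made about it here.

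**Conclusion.** The point holds in limited form. As written, a persisting preoperative urinary infection or fever can be recorded and counted as a postoperative complication. For urinary infection the listed items may not allow this to be undone later; for fever the data are there and only the rule is missing.

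The conclusion rests on the wording of the exposure, the exclusions and the recorded items, and on no assumed rates. It does assume that the case report form follows the listed items, and that either the separate urinary item or the general infection item can bring urinary infection into the complication count.

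The effect on the primary association can be a distortion in either direction. The effect on the secondary objective is an inflated count of urinary infection or fever, with an unknown effect on the ranking. The protocol gives no basis for a size in either case. The correction is worth making because it is cheap and, for the control result, depends on collecting the data prospectively.

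**What to change.** 1. Record the result of the control urine examination whenever one is performed.
2. Code postoperative urinary infection and fever as new, persisting or undetermined against the recorded preoperative status, keeping the level for no sample.
3. Count only new events as complications, and report persisting and undetermined ones separately.
4. State whether the postoperative urinary infection item enters the complication count.
5. Align the two wordings for infection in the POPULATION section and in MONITORED SIGNS AFTER SURGERY.

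The cost is some protocol wording, a classification entry for the two outcomes on the case report form, and one field for the control result. Preoperative fever, preoperative urine findings and the origin of postoperative infection are already listed. The downside is fewer counted events and some judgement in classification, which is why an undetermined category is needed.

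### Does a subject-group line that names only trauma procedures undermine an entry criterion that also admits orthopedic surgery?

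*Protocol*

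**What the plan says.** Five places in the protocol say who is studied.

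- The title: "Urinary Infection and Colonization in Bone Procedures".
- The opening sentence under POPULATION, on patients of 65 or older: "undergoing surgery (bone procedures, traumatology, orthopedics) in acute or elective mode".
- The rationale that closes the POPULATION narrative: "cohort of trauma patients undergoing surgery was chosen to ensure the homogeneity of the studied population (seniors aged 65 and over undergoing bone surgery", where the bracket ends.
- The first line under CHARACTERISTICS OF THE EVALUATION SUBJECT GROUP: "Elective trauma procedures for seniors aged 65 and over, including acute trauma procedures for seniors aged 65 and over".
- The surgical item under ENTRY CRITERIA: "Elective or acute trauma/orthopedic bone surgery".

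What is recorded is set out partly in the POPULATION narrative and partly in the two lists headed MONITORED SIGNS BEFORE SURGERY and MONITORED SIGNS AFTER SURGERY. The narrative adds frailty ("The Clinical Frailty Scale and any administered antibiotic treatment will be recorded") and the hospital course ("trajectory during hospitalization (which departments they will be treated in, including the length of hospitalization) will be recorded"). On timing, the subject-group section says "Recruitment at the time of indication for the procedure or setting the date of surgery", within the pre-anesthetic examination.

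**The concern.** Two things look wrong.

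First, a patient having elective orthopedic bone surgery satisfies the entry criterion but does not appear in the subject-group line. The rationale then claims homogeneity from choosing trauma patients, although the cohort is open to other orthopedic patients and mixes urgent with planned operations. If the population really were unsettled, the study would not know to whom its association applies.

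Second, the study is observational and comparative, and its primary objective is an association between preoperative urinary findings and postoperative complications. Urgency and type of surgery could plausibly relate to both. They can be described, stratified or adjusted for only if they are known for each patient, and no recording statement names either one. If they were truly lost, no later analysis plan could recover them.

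**Working it through.** The protocol gives no sample size, event rate or case mix, so there is no figure to reproduce and no bias to calculate. The check is a comparison of texts.

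**Step 1: the population, place by place.**

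| Place | Type of surgery | Mode |
|---|---|---|
| Title | bone procedures | not stated |
| Opening sentence | bone, trauma, orthopedic | acute or elective |
| Rationale | trauma, glossed in brackets as bone surgery | not stated |
| Subject-group line | trauma | elective and acute |
| Entry criterion | trauma/orthopedic, bone | elective or acute |

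The mode column contains no conflict. The type column has one clear outlier, the subject-group line, and one mixed entry, the rationale.

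**Step 2: size of the mismatch.** If the slash in the entry criterion separates two types, it admits 2 modes × 2 types = 4 groups. The subject-group line names elective trauma and acute trauma, so 2 of 4. There are 10 exclusion criteria: negative urine findings; premedication, alcohol or drugs; sensory impairment; preoperative delirium; severe mental disorder; sopor; coma; septic state; acute respiratory failure; and refusal. None of the 10 concerns the type of surgery. These are counts of labels, not of patients.

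**Step 3: which text decides enrolment.** Patients are admitted through the entry and exclusion criteria. The subject-group line stands under a heading about age, gender, recruitment and reward. It does not say that only trauma qualifies, and it excludes nobody. With that line deleted, the criteria admit exactly the same patients.

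**Step 4: the homogeneity claim.** The rationale says in its own bracket what is homogeneous: the age range and surgery on bone. The entry criteria require both. The sentence does not claim uniform urgency or specialty, and no calculation or stated analysis in the protocol relies on it.

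**Step 5: what silence in the lists means.** The two lists concern clinical signs. They do not mention age or sex, which any description of the cohort needs. They also omit the Clinical Frailty Scale, which a secondary objective requires and which only the narrative says is recorded. Absence from the lists is therefore weak evidence that an item goes uncollected. Staff must know the operation to judge whether it meets the surgical entry criterion, and recruitment happens when surgery is indicated or scheduled, when urgency should also be known.

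**The case for a change.** The strongest argument for a change is that eligibility and prospective data collection belong in the protocol, not in an analysis plan. The protocol itself sets traumatology and orthopedics side by side as separate words, so calling the whole cohort trauma is at least careless. In a non-randomised comparison, urgency is an obvious candidate for adjustment. Knowing the operation at screening is also not the same as coding it: all four groups are eligible, so nobody has to write down which one a patient belongs to. Departments visited are at best a rough proxy for type and do not give mode. The remedy would cost a few words and two data fields.

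Part of this stands. The mismatch on type is real, and a protocol that listed urgency and type among its baseline items would be clearer. What does not stand is the step from an unlisted item to an unrecorded one: the lists leave out other items that are plainly needed, so they cannot carry that inference. Nor does the protocol commit to an unadjusted analysis. The choice of covariates is commonly left to an analysis plan, which is not at hand here. Low cost makes an addition reasonable to suggest, but it does not make its absence an error.

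**Conclusion.** The concern does not call for a change. What remains is a loose description: the subject-group line, and in part the rationale, use trauma where the opening sentence and entry criterion say trauma and orthopedic. Its extent is 2 of 4 labelled groups not named in one descriptive line, with no change in who is eligible. There is no contradiction on acute versus elective surgery. The homogeneity claim, read with its own bracket, is met by the criteria.

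The silence on urgency and type is a gap that a study team and statistician can be expected to fill sensibly. Neither loss of these data nor confounding by them is shown, and the documents give no figures from which to gauge either.

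The conclusion rests on two assumptions. The first is that the entry criterion governs enrolment, as the title and opening sentence support. If the sponsor meant trauma patients only, the entry criterion and opening sentence would be the texts in error and the point would matter. The second is that urgency and type of operation remain available for each patient, which is likely given when recruitment takes place but is not stated. Aligning the wording and naming the two items would be optional clarifications.

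### No patient with clean preoperative urine is enrolled, so the primary objective should be limited to urinalysis-positive patients and should name its contrast

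*Protocol*

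**What the plan says.** Under Primary Objective, the protocol sets out "to determine the relationship between the preoperative occurrence of urinary infection or colonization in patients within the last 30 days before the procedure"; the outcome on the other side of that relationship is a set of complications after surgery. Type of Study reads "monocentric, prospective, comparative, observational". The Population section describes older patients having acute or elective bone surgery and mentions no restriction to abnormal urine.

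The Entry Criteria require a test, not a particular result: "Urine examination as part of pre-anesthetic examination, urine + sediment, in case of suspicion - bacteriological examination". The Exclusion Criteria then remove patients with "Negative urine findings: chemical + sediment examination preoperatively".

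Culture is a second step. Monitored Signs before Surgery states: "in case of positive findings (bacteriuria, pyuria, leukocyturia), collection for bacteriological examination will be indicated". The same section records "whether the infection/findings in the urine were treated or not" and whether a control urine examination was done. No separate control group is described.

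**The concern.** A relationship between the occurrence of a condition and later complications needs patients in whom the condition did not occur. For a study of older patients having bone surgery, a reader would expect many of these to be patients with normal urine. The exclusion removes all of them.

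What is at stake is the conclusion. If the report states that preoperative urinary infection or colonization is, or is not, associated with complications in this surgical population, readers will take the comparison to be with patients whose urine was clean. The data cannot support that. A later analysis plan can choose a reference group among enrolled patients, but it cannot recover patients who were never enrolled.

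**Working it through.** The protocol shown gives no sample size, prevalence, culture yield or event rate, so there is no stated figure to reproduce. The main step is logical; the arithmetic after it is illustrative.

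**Step 1. Who is enrolled, by urine result**

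| Preoperative chemistry and sediment | Culture | Enrolled? | Exposure status |
|---|---|---|---|
| Negative | not triggered | No (excluded) | never observed |
| Positive | positive | Yes | exposed (infection or colonization) |
| Positive | negative | Yes | no proven infection or colonization, but selected on abnormal urine |
| Positive | no result | Yes | unknown |

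The number enrolled from the first row is 0 at any sample size. The last row can occur because culture is indicated rather than required for entry.

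**Step 2. What the missing row hides**

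Let p1 be the complication risk in exposed patients and p0 the risk in clean-urine patients. OR = [p1/(1−p1)] / [p0/(1−p0)]. Assume p1 = 0.30, so the odds are 0.30/0.70 = 0.4286.

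- p0 = 0.10: 0.4286/0.1111 = 3.86
- p0 = 0.20: 0.4286/0.2500 = 1.71
- p0 = 0.30: 0.4286/0.4286 = 1.00

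The enrolled data are the same in all three cases, because p0 is not observed.

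**Step 3. What the enrolled cohort can estimate**

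Assume 150 urinalysis-positive patients, all cultured, with risks of 30% (culture-positive) and 20% (culture-negative). SE(log OR) = √[1/(n1·p1) + 1/(n1(1−p1)) + 1/(n0·p0) + 1/(n0(1−p0))].

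- 70% culture-positive, 105 vs 45: √(1/31.5 + 1/73.5 + 1/9 + 1/36) = √0.1842 = 0.429
- 50% culture-positive, 75 vs 75: 0.383
- 80% culture-positive, 120 vs 30: 0.498

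If 10% to 30% of the 150 had no culture result, 15 to 45 patients would have unknown exposure, and these standard errors would be larger.

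**Step 4. The alternative of enrolling urine-negative patients**

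Keep a total of 150, split into 75 urinalysis-positive and 75 urine-negative, with the same risks (20% now being the clean-urine risk). Only culture-positive patients count as exposed.

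- 70% culture-positive, 52.5 vs 75: √(1/15.75 + 1/36.75 + 1/15 + 1/60) = √0.1740 = 0.417
- 50%, 37.5 vs 75: 0.459
- 80%, 60 vs 75: 0.403

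At 70%, 75 − 52.5 = 22.5 patients with abnormal urine and a negative culture fall in neither group. Keeping 150 urinalysis-positive patients and adding 150 urine-negative ones (105 vs 150) gives 0.295, with 300 patients to follow instead of 150.

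At equal total size, neither design is uniformly more precise. They differ in the question they answer.

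**The case against.** The strongest counter-argument is that the cohort may have been limited to abnormal urine on purpose. The exposure is infection or colonization, not abnormal urinalysis, so patients with abnormal urine and a negative culture are a legitimate group without proven exposure. Two secondary objectives concern colonized and infected patients separately, which suits such a cohort, and an infection-versus-colonization contrast would satisfy the comparative label. The choice of reference group is commonly left to the analysis plan, which is not at hand. The statement in the Population section that the cohort was chosen "to ensure the homogeneity of the studied population (seniors aged 65 and over undergoing bone surgery" explains the type of surgery; that section does not list the other exclusions either, so its silence on urine is not in itself a contradiction.

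Much of this stands. A reader might infer that presence versus absence of infection or colonization cannot be compared at all. The documents do not support that: Step 3 shows a workable, though selected, contrast. What remains is that the objective carries no limit to urinalysis-positive patients, while eligibility imposes one. That limit is set by the protocol, and no analysis plan can lift it afterwards.

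A reader might also infer that patients infected and treated within the 30-day window, whose urine has since cleared, are excluded although exposed. That depends on which test the exclusion refers to. Recruitment may take place when surgery is indicated or its date is set, with a control urine later; a patient positive at the earlier test could then be enrolled. The protocol does not say, and gives no frequency, so this is an ambiguity to settle rather than a demonstrated loss.

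**Conclusion.** The point holds in a limited form and should be fixed. The firm result follows from the text alone: 0 patients with clean preoperative urine are enrolled, so their complication risk, and any effect measure against them, cannot be estimated. The odds ratios and standard errors rest on assumed risks, culture yields and sample sizes, and serve only to show the kind of uncertainty involved.

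The cohort remains usable for comparisons within urinalysis-positive patients, for the two objectives on the most common complication, and for describing antibiotic therapy. The frailty objective is also feasible, but only for urinalysis-positive patients. The study is not invalid; its primary objective is worded more widely than its eligibility allows.

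**What to change.** Keep the exclusion and change the wording:

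- State that the primary objective and its conclusion apply to urinalysis-positive patients aged 65 and over having bone surgery.
- Name the contrast: culture-positive versus culture-negative, and infection versus colonization.
- Report patients without a culture result as a separate group.
- Make no claim against patients without urinary findings.
- State whether the exclusion refers to the initial or a later control urine test, so that patients infected and treated within the 30-day window are handled consistently.

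This costs text only: no extra patients or tests. The price is a narrower conclusion.

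If the sponsor wants the contrast with clean urine, the exclusion has to be removed and urine-negative patients enrolled as a named reference group. No new preoperative test is needed, since urine chemistry and sediment are already routine, but this is a larger design change. Under the assumptions above it means about 52 instead of 105 exposed patients at a total of 150, or follow-up of 300 patients. The reference group would not be cultured, so exposure would be ascertained differently in the two groups, and a place would have to be defined for patients with abnormal urine and a negative culture.
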